3.10.2.3 Patient Perception of Bladder Condition (PPBC – Appendix V)

The PPBC is a validated, patient-reported, single question measure of OAB severity.³⁵ This measure has demonstrated validity, but also good responsiveness to change. It consists of one single question with 6 possible answers, in which the subject is asked to indicate if his or her bladder dysfunction cause him or her no problems at all, or very minor, moderate, severe, or very severe problems.

3.10.2.4 Parkinson's Impact Scale (PIMS – Appendix VI)

There are 10 areas (self, feelings, family, community, work, travel, leisure, safety, financial security and sexuality) in the validated, self-reported, Parkinson's Impact Scale (PIMS)³⁶, with four identified factors:

- psychological
- social
- physical
- financial

Subjects are asked to consider how much impact their Parkinson's symptoms have had on each area of the PIMS, scored from 0 to 4 points. There is a maximum possible score of 40, with higher scores indicating greater impact. This is one of six quality of life scales

recommended by the Movement Disorder Society for use in Parkinson's Disease. Administration time is approximately 5-10 minutes.

3.10.2.5 Epworth Sleepiness Scale (Appendix VII)

The Epworth Sleepiness Scale has been used repeatedly in PD and is one of the best available methods to measure excessive daytime sleepiness in these patients.^{37,38} It is comprised of 8 everyday activities (such as 'Watching TV') and the respondent is to determine the chance of dozing or sleeping during the activity. There are four possible responses ranging from 0 to 3 points. The maximum possible score is 24, with higher scores indicating a greater chance of dozing or sleeping during activities. Self-reported administration times is approximately less than 5 minutes.

3.10.2.6 Parkinson's Fatigue Scale (Appendix VIII)

The Parkinson's Fatigue Scale³⁹ is a 16-item self-report instrument designed to measure the physical aspects of fatigue and its impact on the patient's daily function. Each item has four possible responses ranging from 1 to 5 points, with higher scores indicating greater fatigue. An average score of greater or equal to 2.95 optimally distinguished those who experienced fatigue from those who did not. Administration time is approximately 5-10 minutes.

3.10.3 Procedures related to exploratory analyses

3.10.3.1 Orthostatic Blood Pressure and Heart Rate measurements

Supine blood pressures (systolic and diastolic) will be obtained after 5 minutes of reclining, along with heart rate. Immediately following these measurements the subject will arise to full standing position, and systolic and diastolic blood pressures and heart rate will be obtained at 3 minutes after arising. Supine measurements will be obtained with the subject reclining with the head elevated at 30° from the horizontal. If the investigator determines that the subject will be unable to stand for 3 minutes, then standing measurements will be obtained as close to the 3 minute time as possible. Blood pressure measurements will be obtained manually using a sphygmomanometer, always using the same side upper extremity for each subject (either left or right, but always the same side in the same subject). 40

Heart rate will be manually counted for 30 seconds in the radial artery on the same side, and will be obtained after the blood pressure measurement. Presence of orthostatic hypotension will be documented for a drop in systolic blood pressure equal or greater

than 20 mm Hg, or in diastolic blood pressure equal or greater than 10 mm Hg. Symptomatic orthostatic hypotension will be documented if the subject also experiences presyncopal or syncopal symptoms.

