During the 2-week run-in placebo period all subjects will receive placebo tablets matching the 25 mg mirabegron extended release tablets. During the first two weeks of the double-blind placebo-controlled phase, subjects will be randomized to either 25 mg extended release mirabegron or matching placebo (2:1 ratio). During the following 10 weeks of the double-blind placebo-controlled phase, subjects tolerating treatment without side-effects will be escalated to 50 mg mirabegron (two 25 mg mirabegron extended release tablets) or matching placebo (two placebo tablets); subjects experiencing side-effects that do not preclude continuation of the study will continue at the dosage level of one 25 mg extended release mirabegron tablet or matching placebo daily. Subjects who have escalated to 50 mg mirabegron or matching placebo and experience side-effects at that level, will be allowed one dose reduction to 25 mg mirabegron or matching placebo.

Depending on dose level, one or two tablets will be administered daily, with or without food, swallowed whole with water; chewing, crushing or dividing is not allowed.

Primary Endpoint:

Relative mean change to the MoCA score between randomization visit (Visit 3) and week 14 visit (Visit 7).

Table 1. Schedule of Activities:

VISIT/PROCEDURE:	Screening Visit	Baseline Visit	Randomizati on	Low dose phase	Dose escalation	High dose phase	End of TX / Early Term	Follow-up / Week 16
	V 151t					•		
Visit number	1	2	3	4 phone	5	6	7	8
Visit time	week -4 to -6	week -2	day 0	day 7	day 14	day 42	day 84	day 98
Informed consent	X							
Inclusion/Exclusion criteria	X							
Past history/demographic	X							
Neurological and physical exam	X	X			X		X	X
Urologic exam	X *				X*			X*
Cystoscopy	X*							
Concomitant medication	X	X	X	X	X	X	X	X
Adverse events		X	X	X	X	X	X	X
Study drug compliance			X	X	X	X	X	
UPDRS	X				X		X	X
Vital signs (includes weight, height and orthostatics)	X	X	X		X		X	X
ECG	X				X		X	
Pregnancy test (for WOCP)	X							X
Urinalysis	X*				X*		X	X*
Blood samples (safety)	X						X	
OABQ	X		X		X	X	X	
3-day VD training and concordance	X							
3-day VD assessment		X	X		X	X	X	
PVR	X*				X*			X*
PPBC		X	X		X	X	X	X
CQ			X				X	
UPDRS-6			X				X	
MoCA	X		X				X	
Map Search			X				X	
HVLT			X				X	
TMT A and B			X				X	
BAI			X				X	
BDI-II			X				X	
ESS			X				X	
PFS			X				X	
PIMS			X				X	
Drug dispense		X	X			X		

^{*} Procedures performed during the urology visit

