3.9 Visit and assessment schedule

3.9.1 Screening (Visit 1)

Written informed consent will be obtained before any study specific procedures are undertaken. Visit 1 has to be completed at least 2 weeks and no longer than 4 weeks prior to baseline visit, to allow sufficient time to review collected information and determine subject eligibility for participation. Urology screening procedures (urologic examination with cystoscopy, urinalysis and PVR) can be conducted anytime between Visit 1 and one week prior to baseline, including the same day as visit 1, but procedures for visit 1 have to precede urology visit.

Screening visit 1 will be conducted by the Investigator, or his designee, and will include:

- Review and signing of the written informed consent
- Assignment of patient identification number
- Review of inclusion and exclusion criteria

- Demographics
- Review of medical history
- Review of concomitant medications
- Vital signs, including weight, height, and orthostatics
- Physical examination
- Neurological Examination
- Unified Parkinson's Disease Rating Scale (UPDRS)
- 12-lead ECG recording
- Blood samples for chemistry and hematology (Na, K, Cl, HCO₃, blood glucose, BUN, creatinine, GFR, AST, ALT, total bilirubin, Alkaline phosphatase, GGT, CBC with differential and platelets)
- Montreal Cognitive Assessment (MoCA)
- Overactive Bladder Questionnaire (OABQ)
- 3-day VD training and concordance
- Serum pregnancy test (SPT) for WOCP
- Urologic examination with cystoscopy
- Urinalysis
- Post-void residual

All screening visit results must be reviewed by the Investigator or designee prior to Visit 2. In cases of screen failure resulting from treatable and reversible causes (e.g. urinary tract infection, other intercurrent illness during the screening period, etc.) or scheduling conflict, the screening period can be extended up to 56 days at the Investigator's discretion, provided subject still meets eligibility criteria. Screening assessments may need to be repeated at the Investigator's discretion.

3.9.2 **Baseline (Visit 2; Day -14)**

The baseline visit (Visit 2) will occur 14-28 days from Screening visit 1. Procedures will be conducted by the Investigator or designee:

- Concomitant medications
- Adverse events
- Vital signs, weight, height, and orthostatics
- Physical Examination
- Neurological Examination
- 3-day VD assessment
- Patient Perception of Bladder Condition (PPBC)
- Study drug dispense

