7.4.3 Summary of exploratory data

The exploratory objectives are to assess effects of mirabegron on orthostatic changes in blood pressure, depressive and anxiety symptomatology, excessive salivation, constipation and PD motor symptom severity in PD patients with OAB symptoms and CI. The related hypotheses are that mirabegron will not impact these symptoms. The goal is to demonstrate equivalent symptoms prior to and following treatment with mirabegron as well as change compared to the placebo group. Tests of equivalence will be performed using the two one-sided tests approach on change from visit 3 to visit 7 in related variables within groups as well as between the two groups. Equivalence ranges will be determined for each measure based on available literature prior to data analysis.

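### Between-arm orthostatic comparison: covariate adjustment using the three pre-randomisation sets already scheduled would improve precision at no cost (optional, one exploratory outcome)

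*Combined protocol and SAP*

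**What the plan says.** Section 3.10.3.1 sets the measurement: "Supine blood pressures (systolic and diastolic) will be obtained after 5 minutes of reclining, along with heart rate"; after standing up, "systolic and diastolic blood pressures and heart rate will be obtained at 3 minutes after arising". The method is manual: "Blood pressure measurements will be obtained manually using a sphygmomanometer". No number of readings and no averaging rule is given.

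The vital-signs row of Table 1, "Vital signs (includes weight, height and orthostatics", is marked at Visits 1, 2, 3, 5, 7 and 8. The visit lists agree: "Vital signs, including weight, height, and orthostatics" at screening (3.9.1) and "Vital signs, weight, height, and orthostatics" at baseline (3.9.2). Visit 3 repeats the set (3.9.3).

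Section 7.4.3 applies the "two one-sided tests approach on change from visit 3 to visit 7 in related variables", within and between groups. It does not name the orthostatic variable and leaves the margin to be set before data analysis. Section 3.9.3 makes Visit 3 the analysis baseline. Outside the tests, 7.4 provides only descriptive summaries by visit.

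**The concern.** As 3.10.3.1 is written, each subject's systolic (or diastolic) outcome is a difference of two differences, built from four manual readings: supine and standing at Visit 3, supine and standing at Visit 7. Visit-to-visit noise in the Visit 3 value passes in full into an unadjusted change score. Two further pre-randomisation values of the same quantity will be on file and are not used, and neither is the correlation between baseline and outcome.

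With 20 and 10 subjects fixed by feasibility (7.1), the analysis is the main remaining means of narrowing the interval, and an equivalence test passes only if that interval fits inside the margin. No other exploratory measure in Table 1 has three pre-randomisation assessments.

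**Working it through.** **Inputs from the documents.** 20 active and 10 placebo subjects (7.1); significance level 0.05 (7.4); orthostatics at Visits 1, 2, 3 and 7; Visit 1 is 2 to 4 weeks before Visit 2 (3.9.1), which is 2 weeks before Visit 3. There is no plan figure to reproduce: no SD, between-visit correlation, margin or power is given for this outcome.

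**Notation.** D = standing minus supine pressure at a visit, with variance s² at each visit and correlation r between visits.

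**Step 1. Equal correlation across visits, no variation between subjects in true change.**

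- Planned change score: Var(D7 − D3) = 2(1 − r)s²
- Change from the mean of Visits 1 to 3: (1 + 1/3)(1 − r)s²
- ANCOVA on Visit 3: (1 − r²)s²
- ANCOVA on the mean of Visits 1 to 3: [1 − 3r²/(1 + 2r)]s²

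| Variance in units of s² | r = 0.3 | r = 0.5 | r = 0.7 |
|---|---|---|---|
| Planned change score | 1.400 | 1.000 | 0.600 |
| Change from 3-visit mean | 0.933 | 0.667 | 0.400 |
| ANCOVA, Visit 3 | 0.910 | 0.750 | 0.510 |
| ANCOVA, 3-visit mean | 0.831 | 0.625 | 0.388 |
| Saving against plan: ANCOVA, Visit 3 | 35% | 25% | 15% |
| Saving against plan: ANCOVA, 3-visit mean | 41% | 38% | 35% |
| Extra saving from adding Visits 1 and 2 to ANCOVA | 9% | 17% | 24% |

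Example at r = 0.5: 1 − 0.625/1.000 = 37.5% against plan, and 1 − 0.625/0.750 = 16.7% against ANCOVA on Visit 3. Averaging within a simple change score saves 1 − (4/3)/2 = 33.3% at every r.

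**Step 2. Cost of estimating the slope.** With 28 residual degrees of freedom before adjustment and a roughly normal covariate, the variance of the adjusted difference is inflated on average by 1 + 1/26 = 1.038. The net savings against plan become 33 to 38% for the 3-visit mean (for example 1 − 0.594 × 1.038 = 38% at r = 0.3) and 12 to 33% for Visit 3 alone. The 9 to 24% increment does not change, because both ANCOVAs pay this cost.

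**Step 3. In mmHg.** Assume s = 12 mmHg. The 90% CI half-width is t × 12 × √(variance in the table) × √(1/20 + 1/10), with t = 1.701 (28 df) for the change score, and t = 1.703 (27 df) with the Step 2 factor for ANCOVA.

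| Half-width, mmHg | r = 0.3 | r = 0.5 | r = 0.7 |
|---|---|---|---|
| Planned | 9.4 | 7.9 | 6.1 |
| ANCOVA, Visit 3 | 7.7 | 7.0 | 5.8 |
| ANCOVA, 3-visit mean | 7.4 | 6.4 | 5.0 |

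All half-widths scale in proportion to s.

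**Step 4. Relaxing the assumptions.** Visits were placed at weeks −5, −2, 0 and 12. Correlation decayed with a half-life of 4 or 12 weeks, 0 to 75% of the non-noise variance was stable, and 0, 30 or 50% of total variance was visit-level noise.

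- ANCOVA on the 3-visit mean had lower residual variance than the planned change score in every case, by 5 to 47%. At the 5% end, the Step 2 cost leaves about 1%.
- Against ANCOVA on Visit 3, the extra visits ranged from a 4% loss to a 14% saving. In settings with half-lives up to 26 weeks the loss reached 7%.
- Averaging in a simple change score saved from nothing (−0.5%) to 12% without visit-level noise, and 15 to 30% with it.
- If true change varies between subjects, by 0.5 to 4 times the visit-level variance, the 33% for the simple change score falls to 27% down to 11%.

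**The case against.** Visit 3 is a deliberate and uniform baseline. Section 3.9.3 names it for all outcomes, and it follows a run-in meant to reduce the placebo effect, whereas Visits 1 and 2 precede that run-in. This stands: a single post-run-in baseline is legitimate, and nothing here shows an error or a bias in the plan.

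A reader might infer that about a third of the variance is simply avoidable because two sets are ignored. The documents do not support that. They give no correlation, the one-third figure needs equally correlated visits and little variation in true change, and it is close to a ceiling for averaging in a change score. Decay is plausible: Visit 1 is 4 to 6 weeks before randomisation, and screening may be extended to 56 days (3.9.1). Much of the gain is ordinary covariate adjustment; at r = 0.3, Visit 3 alone as covariate saves 35%.

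A reader might also infer that the protocol prescribes single readings. It is silent on replicates; single readings are how the text reads, not what it states. Nor is orthostatic pressure the main rationale: section 1.3 leads with cognition, and the objective is exploratory.

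One cost is real. With different baselines, the within-arm changes will not subtract to the between-arm estimate. The between-arm comparison itself is safe, because every covariate reading precedes randomisation. Within-arm tests would be exposed to a run-in shift, and to regression to the mean from the supine blood pressure exclusion, so they should stay on Visit 3.

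**Conclusion.** The point holds as an optional improvement to precision. For a continuous systolic or diastolic orthostatic change, the planned unadjusted change score is less efficient than an ANCOVA built from readings already scheduled. Its size under equal correlation is as tabulated in Step 1; the benefit of adjusting is the more dependable part, and the benefit of adding Visits 1 and 2 depends on how far correlation decays over time.

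It would go too far to say that this choice decides whether the orthostatic question can be answered: that depends on an SD and a margin that the plan does not give, and withdrawals are excluded from analysis (7.3), so fewer than 30 subjects may contribute. The calculation does not apply if the tested variable is the yes/no orthostatic hypotension also defined in 3.10.3.1. Because 7.4.3 does not say which variable is tested, it should be named in any case.

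**What to change.** In 7.4.3:

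1. Name the tested variables as standing-minus-supine systolic and diastolic pressure.
2. For the between-arm comparison, take the two one-sided tests from the 90% CI of the treatment effect in an ANCOVA, with the Visit 7 value as outcome and the mean of the Visit 1, 2 and 3 values as covariate. Apply the Shapiro-Wilk check of 7.4 to the residuals.
3. Repeat with Visit 3 alone as covariate, as a sensitivity analysis.
4. Keep within-arm tests on the Visit 3 to Visit 7 change, and note that they will not subtract to the adjusted between-arm estimate.
5. State how many readings are taken per position and, if more than one, how they are combined.

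Items 1 to 4 are SAP wording, can be fixed at the same pre-analysis step as the margins, and need no new visit or reading. Item 5 is one clarifying sentence in 3.10.3.1.

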3.10.3.2 Beck Depression Inventory version II (BDI-II – Appendix IX)

The Beck Depression Inventory⁴¹ (BDI) has been used in a number of studies in Parkinson's disease and is an established screening tool that reliably discriminates depression from anxiety in various populations. It consists of 21 questions scored from 0-3 with higher scores indicating greater severity; a total score of all 21 questions provides an indicator of depressive symptomatology. Administration time is approximately 5-10 minutes. Interpretation guidelines for the BDI^{41,42}:

- 0-9 Normal range
- 10-15 Minimal depressive symptomatology
- 16-19 Mild-moderate depressive symptomatology
- 20-29 Moderate-to-severe depressive symptomatology
- 30-63 Severe depressive symptomatology

Scores greater than 15 may indicate symptoms of depression which may impair cognitive abilities.

3.10.3.3 Beck Anxiety Inventory (BAI – Appendix X)

The Beck Anxiety Inventory⁴³ (BAI) was developed to address the need for an instrument that would reliably discriminate anxiety from depression while displaying convergent validity. The scale consists of 21 items, each describing a common symptom of anxiety. The respondent is asked to rate how much he or she has been bothered by each symptom over the past week on a 4-point scale ranging from 0 to 3. The items are summed to obtain a total score that can range from 0 to 63 (higher scores indicate greater anxiety). The scale has high internal consistency and item-total correlations ranging from .30 to .71 (median=.60). Administration time is approximately 5-10 minutes.

3.10.3.4 Constipation Questions (CQ – Appendix XI)

Subjects will be asked a series of 6 questions to establish if they meet the Rome II criteria for constipation.⁴⁴ The Rome II committee defined functional constipation as occurrence of 2 or more of the symptoms listed in Appendix XI for at least 12 weeks, which need not be consecutive, in the preceding 12 months and in the absence of structural and biochemical explanation. The criteria exclude subjects presenting with loose stool episodes and irritable bowel syndrome. For the purpose of this study, the reference period will be the preceding 2 weeks to conform with the timeline of the study. The questions will be administered by the investigator or designee.

3.10.3.5 Unified Parkinson's Disease Rating Scale (UPDRS) – Appendix XII

The UPDRS assesses motor and functional abilities of the subjects. ⁴⁵ The total UPDRS will be completed (defined for this study as the sum of Parts I, II, III, and IV (I-Mentation, behavior, and mood section; II-Activities of Daily Living (ADL); III-motor section; and IV-complications section) will be completed by history and examination. The UPDRS parts III and IV evaluation will be conducted by a trained neurologist or other senior trained research staff with at least 10 years' experience in conducting the UPDRS. All attempts will be made to ensure that the same trained research staff member performs the UPDRS parts III and IV at all visits for each subject and at approximately the same time of the day and time following administration of medication. The UPDRS parts I and II may be completed by trained research staff as delegated by the PI.

3.10.3.6 Excessive Salivation Question (Unified Parkinson's Disease Rating Scale Question 6 - UPDRS-6) – Appendix XII

This is question 6 on the UPDRS⁴⁵ which refers specifically to excessive salivation. It is rated 0-4 and can be self-administered.

3.11 Safety assessments

3.11.1 Physical Examination and Neurological Examination

A complete physical exam (consisting of a review of all body systems) and neurological exam (including evaluation of mental status; motor function; balance and coordination; sensory function; reflexes and cranial nerves) at screening and end of treatment/early termination (visit 7) will be conducted by the study neurologist (primary investigator or sub-investigator). On other visits (baseline, dose escalation (visit 5), follow-up (visit 8) and unscheduled visit) a symptom-directed physical and neurological exam will be performed by the study neurologist.

3.11.2 12-Lead Electrocardiography

12-lead ECG's will be performed to evaluate the cardiovascular system. A standard 12-lead ECG will be performed at screening, dose escalation (visit 5) and end of treatment/early termination (visit 7). Additional ECGs will be performed if clinically indicated. ECGs will be conducted after approximately 5 minutes supine or recumbent rest using a standard ECG machine equipped with computer-based interval measurements.

The Investigator is responsible for evaluating the ECG. ECG findings will be assessed by the Investigator as normal, abnormal not clinically significant (NCS), or abnormal clinically significant (CS), as appropriate. All abnormalities, whether assessed as clinically significant or not, will be recorded. The ECG tracing should be initialed and dated by the Investigator.

3.11.3 Urologic examination

The urologist will exam the subject for organic causes of OAB and to determine if the subject has bladder outlet obstruction (BOO). The urologist will also perform cystoscopy during screening and obtain post-void residuals.

3.11.4 Post-void Residual (PVR)

The post-void residual (PVR) urine test measures the amount of urine left in the bladder after urination. The test is used to help evaluate incontinence in women and men, problems with urination, and benign prostatic hyperplasia. The amount of leftover (residual) urine will be measured using cystoscopy or ultrasound.

3.11.5 Vital signs and weight

Blood pressure and heart rate will be measured as described in section 3.10.3.1. Height will be performed at screening only and weight will be measured at all visits.

3.11.6 Clinical laboratory parameters

The safety laboratory tests (hematology, chemistry and urinalysis tests) will be performed as general measures of health. Methodist Hospital Laboratory services will be responsible for testing of all laboratory samples. Instructions will be included in the laboratory manual. Any clinically important abnormal laboratory values noted at the Screening visit will be recorded as medical history. In addition, in order for the Sponsor to collect additional information about clinically important laboratory abnormalities, at minimum, the following laboratory abnormalities should be captured at Unscheduled Visits or End of Treatment/Early Term on the non-serious or serious AE pages of the CRF as appropriate:

- Any laboratory test result that meets the criteria for an AE or SAE;
- Any laboratory abnormality that requires the subject to have study drug discontinued or interrupted;

• Any laboratory abnormality that requires the subject to receive specific corrective therapy.

All clinically important abnormal laboratory tests occurring during the study will be repeated in appropriate intervals until (1) the value returns to Baseline, (2) the value is judged to be clinically acceptable by the Investigator, (3) a diagnosis that explains the abnormal laboratory is made or (4) subject is lost to follow-up. When possible, the Investigator should report the clinical rather than the laboratory term (e.g., anemia versus low hemoglobin.)

